5.1 Data collection

The case report forms (CRFs) will serve as the means to document and collect clinical data throughout the trial. These forms will be in physical paper format, ensuring that the original material remains intact. It is important to note that the CRFs should not be altered or modified arbitrarily.

All pertinent information regarding the patients involved in the trial will be recorded accurately and promptly on the CRFs. This includes any relevant data related to their medical condition, treatment received, and any observed outcomes or adverse events. It is crucial that this information is recorded truthfully to maintain the integrity and validity of the trial results.

Data collected on site will be entered on a real-time basis using the EDC system to ensure that all required items are entered. The EDC will automatically verify that there are no missing values during submission. After examinations are completed, the paper examination forms will be stored in a locker of the research center to protect the privacy

of participants and ensure access for data review and audit.

5.2 Statistical analysis plan

The intention-to-treat (ITT) population comprised participants randomly assigned to either group. Data from all participants who attended at least one subsequent follow-up visit were included in the analysis, regardless of treatment or follow-up visit compliance. No imputation was used for the missing data. Individuals who switched to other myopia treatment modalities, such as orthokeratology or atropine eye drops, or discontinued the RLRL treatment, were censored. If a participant had only one eye with a SER exceeding -4.0 D, that eye was selected for the statistical analysis. In cases where both eyes were exceeding -4.0 D, the right eye was chosen for the analysis.

Treatment efficacy was assessed using longitudinal mixed models for primary (changes in AL) and secondary (changes in SER and IOP) outcomes at multiple follow-up visits. The mixed effects model was fitted with a random intercept and random slope for the participant, where the group, visit, group-by-visit interaction, baseline age, sex, and baseline AL were fixed effects. Estimated mean treatment differences and corresponding 95% confidence intervals (CIs) were derived from mixed models. UCVA alterations were classified into three categories: decline by two or more lines, stable (within a line), or improvement by two or more lines. The BCVA at the 12-month and baseline was evaluated against the 20/25 standard.

Sensitivity analyses were conducted to assess the treatment effects of therapy in controlling myopia progression, specifically axial elongation and SER progression, across different baseline SER and age groups.

A longitudinal mixed-model analysis was conducted to assess the relationship between treatment efficacy and compliance within the intervention group. Treatment compliance in the intervention group was measured as a percentage of the total number of assigned treatment sessions.

Safety analyses were performed in the ITT population. All adverse events were reported individually. Six ophthalmologists, one from each center, independently scrutinized the OCT scans for potential structural anomalies.

6.MONITORING

Monitoring begins immediately after initiation. The first case from each participating center is enrolled, followed by monitoring at 30% and 50% of enrollment, and finally after completion of enrollment. The duration of surveillance is determined by the occurrence of serious adverse events. If there are abnormal enrollment situations or a high frequency of program violations, the frequency of monitoring will be increased accordingly. The monitoring focuses on subjects, investigators, and equipment used, primarily assessing the following aspects:

1. Informed consent status: Ensuring that the number of signed informed consent forms matches the number of cases in the clinical trial report (including cases of screening failure), verifying that the version of the signed informed consent form aligns with the version approved by the ethics review, confirming that the ethics review was conducted prior to the signing of the informed consent form, assessing the completeness and standardization of the informed consent form (including inclusion of the clinical trial personnel's contact information, signing date, etc.), and verifying that the subject's signed informed consent form was signed by the subject or their legal representative (if necessary, confirming the actual participation of subjects in the trial).
2. Implementation assessment: Whether the clinical trial procedures adhere to the clinical trial protocol, including the subject selection and exclusion criteria, sample size, selection of control devices, trial duration, observation endpoints, and the management and documentation of adverse events; verifying that the original data collection and case report forms are signed by the clinical trial personnel.
3. Equipment assessment: Whether the delivered equipment product has a valid product inspection report issued by a qualified testing agency, and whether the management record of the tested product (including transportation, reception, processing, storage, distribution, recycling, and disposal) is complete; verifying if the quantity is consistent; assessing if the transportation conditions, storage temperature, storage conditions, storage duration, and safety validity period of the tested product meet the requirements; confirming if the tested product matches the product name, specification, and model

stated in the test report and clinical practice report. After each inspection, the inspector will generate an inspection report based on the findings.

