Eligibility criteria:

Inclusion criteria:

- ① Age 6-16 years old, no gender limit;
- ② Either eye meets the diagnosis of myopic refractive error and the myopia of cycloplegic spherical equivalent refraction (SER) at least -4.0 D, astigmatism 2.0 D

or less, anisometropia 3.0 D or less, and best-corrected visual acuity (BCVA) of LogMAR 0.2 or better.

- ③ Have normal thinking and language communication skills, and be able to actively cooperate with the required treatment;
- ④ No contraindications to the treatment of atropine such as acute ocular inflammation, dry eye, keratoconus, diabetes, etc.;
- ⑤ Written informed consent of the guardian and the child.

Exclusion criteria:

1. History of photosensitivity, glaucoma, glaucoma syndrome, ocular hypertension, and macular pathology or damage in the fundus;
2. The average K value of the anterior surface of the cornea is ≥ 45 in corneal curvature examination;
3. Patients with systemic diseases such as heart, liver, kidney, and congenital hereditary myopia;
4. Patients with chronic eye diseases such as eye trauma and strabismus or surgical eye, atopic keratoconjunctivitis;
5. People who have had other eye diseases such as inverted trichiasis, severe corneal and conjunctival infections in the past;
6. People with neurological diseases and allergies or contraindications to atropine drugs or other therapeutic drugs;
7. Patients with immune system and systemic diseases such as albinism, psoriasis, nephrotic syndrome, systemic lupus erythematosus, diabetes, etc.;
8. People with epilepsy and mental disorders who cannot communicate normally;
9. Individuals who have previously received other treatments to control the development of myopia, such as the use of anticholinergic drugs such as atropine within 3 months, or participated in other related researches such as functional frame mirrors, multifocal soft mirrors, etc.;
10. Other situations that the researcher judges are not suitable for participating in the study.

Control type:

Comparison of the effect of routine single vision spectacle lenses

Statistical analysis plan:

The intention-to-treat (ITT) population comprised participants randomly assigned to either group. Data from all participants who attended at least one subsequent follow-up visit were included in the analysis. Individuals who switched to other myopia treatment modalities or discontinued the RLRL treatment, were censored.

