3.1 Eligibility criteria

Inclusion criteria

- ① Age 6-16 years old, no gender limit;
- ② Either eye meets the diagnosis of myopic refractive error and the myopia of cycloplegic spherical equivalent refraction (SER) at least -4.0 D, astigmatism 2.0 D or less, anisometropia 3.0 D or less, and best-corrected visual acuity (BCVA) of LogMAR 0.2 or better.
- ③ Have normal thinking and language communication skills, and be able to actively cooperate with the required treatment;
- ④ No contraindications to the treatment of atropine such as acute ocular inflammation, dry eye, keratoconus, diabetes, etc.;
- ⑤ Written informed consent of the guardian and the child.

Exclusion criteria

- ① A history of photosensitivity, glaucoma, glaucoma syndrome, ocular hypertension, and macular pathology or damage in the fundus;
- ② Corneal curvature examination, the average K value of the anterior surface of the cornea is ≥ 45 ;
- ③ Patients with heart, liver, kidney and other systemic diseases and congenital hereditary myopia;
- ④ Patients with chronic eye diseases such as ocular trauma and oblique or surgical eyes, atopic keratoconjunctivitis;
- ⑤ Patients with previous eye diseases such as inverted trichiasis, severe corneal and conjunctival infections;
- ⑥ Patients with neurological diseases and allergies or contraindications to atropine drugs or other therapeutic drugs;
- ⑦ Patients with immune system and systemic diseases such as albinism, psoriasis, nephrotic syndrome, systemic lupus erythematosus, diabetes, etc.;
- ⑧ People with epilepsy, mental disorders and unable to communicate normally;

- ⑨ Those who have previously received other treatments to control the development of myopia, such as the use of anticholinergic drugs such as atropine within 3 months, or participated in other functional frame mirrors, multifocal soft mirrors and other related researchers;
- ⑩ Other situations that the researcher judges are not suitable for participating in the research.

Participant withdrawal or termination

A study investigator will terminate participation in the study for the following reasons:

- 1) The patient receives other myopia control treatments;
- 2) Patients continuously stop using Eyerising equipment for more than 14 days;
- 3) Severe comorbidities or adverse events: patients cannot tolerate light, have obvious eye allergies such as tearing, skin rash, and the after-image time after low-energy laser treatment exceeds 5 minutes;

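### The primary axial-length analysis is presented as intention-to-treat, but it censors children who stop RLRL or switch treatment and so estimates an on-treatment effect

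*Combined protocol and SAP*

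**What the plan says.** Section 5.2 opens with the population: "The intention-to-treat (ITT) population comprised participants randomly assigned to either group". It then says that data from everyone with at least one follow-up visit are "included in the analysis, regardless of treatment or follow-up visit compliance". On missing values: "No imputation was used for the missing data". The next sentence is the censoring rule: "Individuals who switched to other myopia treatment modalities, such as orthokeratology or atropine eye drops, or discontinued the RLRL treatment, were censored". The Abstract repeats it: "Individuals who switched to other myopia treatment modalities or discontinued the RLRL treatment, were censored". No other efficacy population is defined, and censoring is not explained for a mixed model.

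Section 3.1, under participant withdrawal or termination, says: "A study investigator will terminate participation in the study for the following reasons". The first reason is "The patient receives other myopia control treatments". The second is being off the device continuously for more than 14 days, and the third covers intolerance and adverse events.

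The Follow-up Schedule in section 4.2 and the table in section 4.3 list visits to Day 365. They contain no early-termination visit and no follow-up after termination, and the end of the study is marked only at Visit 7.

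The sensitivity analyses in section 5.2 concern treatment effects, "specifically axial elongation and SER progression, across different baseline SER and age groups". None varies the handling of stoppers or switchers.

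**The concern.** An ITT analysis compares the arms as randomised, using outcomes whether or not treatment continued. Section 5.2 announces that population and then removes outcomes because of what happened to treatment. Section 3.1 makes this more than a wording issue: if participation ends at the event, the later AL is never measured and no reanalysis can recover it.

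The rule is also asymmetric. Only the RLRL arm can stop RLRL, and prolonged after-image is specific to the device. Families know their allocation (section 3.3), so switching may differ by arm and may depend on how fast the child's eye is growing.

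At stake is the meaning of the primary result. A reader would take it as the benefit of being assigned RLRL. The model would instead estimate the benefit had every child stayed on the assigned treatment, under an assumption that the plan never tests.

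**Working it through.** **1. The plan's own figure.** Section 3.6 gives alpha 0.05, power 90%, control elongation 0.40 mm, SD 0.40 mm and a 0.20 mm effect. The normal formula gives 2 × (1.960 + 1.282)² × (0.40/0.20)² = 84.06, so 85 per group. The two-sided t-test gives 85.03, rounded up to the stated 86. Then 172/0.9 = 191.1, rounded up to the stated 192. The sample size reproduces. Its only attrition allowance is 10% loss to follow-up, with nothing for stopping or switching.

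**2. The rules side by side.**

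| Event | Section 3.1 | Section 5.2 | AL after the event |
|---|---|---|---|
| Switch to another myopia treatment (either arm) | Participation ends | Censored | Not planned, not used |
| RLRL stopped (RLRL arm only) | Participation ends after more than 14 days off | Censored, no threshold given | Not planned, not used |
| Intolerance or adverse event | Participation ends | Censored if RLRL is stopped | Not planned, not used |

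The natural reading of censoring here is that data up to the event are kept, because every child with at least one follow-up visit is included. A likelihood-based mixed model without imputation then carries the on-treatment course forward implicitly, under missing at random. That is a hypothetical, on-treatment estimand.

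**3. Illustration of the gap.** The documents give no stopping rate, switching rate or elongation rate after stopping, so these are assumptions. A share p of the RLRL arm stops at random, equally often at 1, 3, 6 or 9 months; elongation is then r mm/year; no control switches.

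- Mean stopping time = (1 + 3 + 6 + 9)/4 = 4.75 months, so the off-treatment fraction is f = (12 − 4.75)/12 = 0.604. Without month 9, f = (12 − 3.33)/12 = 0.722.
- As-randomised difference = 0.20 − (r − 0.20) × f × p.

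| Rate after stopping | p = 10% | p = 20% | p = 30% |
|---|---|---|---|
| 0.40 mm/year (control rate) | 0.188 | 0.176 | 0.164 |
| 0.40 mm/year, no month-9 stopping | 0.186 | 0.171 | 0.157 |
| 0.30 mm/year | 0.194 | 0.188 | 0.182 |
| 0.20 mm/year (slowing persists) | 0.200 | 0.200 | 0.200 |

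If 10% of RLRL children stop (control rate afterwards) and 10% of controls switch at random to something that slows elongation by 0.20 mm/year, the difference is 0.20 − 2 × 0.20 × 0.604 × 0.10 = 0.176 mm.

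The standard error with 86 per arm is 0.40 × √(2/86) = 0.061 mm. The gaps above run from 0 to 0.043 mm.

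**4. Simulation check.** Settings: 1,500 runs, 96 per arm, the five planned visits, random RLRL stopping with control-rate growth afterwards, generalised least squares with known covariance, and 50%, 75% or about 100% of the 12-month variance persistent within child. Using data up to the event gave 0.196 to 0.203 mm in every case. Using all data by arm gave 0.187–0.191, 0.175–0.177 and 0.161–0.165 mm at 10%, 20% and 30% stopping (Monte Carlo error about 0.0015). So, under random stopping, the planned rule recovers the on-treatment 0.20 mm and not the effect of assignment.

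**5. Secondary and safety data.** Spherical equivalent is scheduled only at Days 180 and 365. The Day 180 ± 14 window opens at 180 − 14 = Day 166. A child terminated before then has no post-baseline refraction, even after attending the Day 30 and Day 90 visits. Slit-lamp examination and best-corrected acuity are planned at the same two visits, as is OCT, which section 4.2 marks optional.

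**The case against.** Five points can be made for the plan.

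- *The ITT label is tied explicitly only to safety.* Correct: the efficacy paragraph does not use the term. But section 5.2 defines ITT first, states the data rules directly after it and defines no other efficacy population, so no other label is available to the reader.
- *The compliance clause may mean only that no minimum session count applies*, since compliance is later defined as a percentage of sessions. This can reconcile two sentences. It does not reconcile an ITT population with censoring at discontinuation.
- *Sections 3.1 and 5.2 use different triggers* (more than 14 days off against an undefined discontinuation), and no sentence expressly cancels later visits. The first is a further ambiguity to settle. On the second, ending participation with no termination visit leaves little room for another reading.
- *No material effect is shown.* This largely stands. Every stopping input is assumed and the ranges are not bounds. If stoppers lose half to all of the 12-month benefit, 10% to 30% stopping gives 0.19 down to 0.14 mm. Power with 96 per arm at 20% stopping is then 79.1% to 87.7%. Selective switching is not quantified, because the documents do not say how much of the 12-month variance is persistent.
- *An on-treatment estimand is legitimate.* It is, if declared. Parts of the plan are in the past tense, so follow-up may already be over; relabelling would then be the remaining remedy.

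**Conclusion.** The concern holds and must be fixed. As written, the primary AL analysis estimates an on-treatment effect that is valid only under missing at random, while the surrounding text presents it as ITT. The post-event data needed for the effect of assignment are not planned to be collected, and no sensitivity analysis examines the choice. The same rule reaches the secondary refraction analysis.

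The documents fix neither the size nor the direction of the difference. Under random stopping by 10% to 30% of the RLRL arm, with no control switching, the illustrated gap is 0 to 0.043 mm, depending mainly on growth after stopping. That is below one standard error, so nothing here shows that the trial's conclusion would reverse. The conclusion about what is estimated rests on the text and not on those assumptions.

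**What to change.** 1. In section 3.1, separate stopping the device from leaving the study. Keep the already scheduled visits to Day 365 unless consent is withdrawn. The device-stopping criteria themselves are not at issue.
2. In section 5.2 and the Abstract, make the primary analysis use all observed AL by randomised arm, including values after stopping or switching.
3. Define censoring as use of data up to the event, reconcile its trigger with section 3.1, and keep that analysis as a labelled on-treatment supplement.
4. Report stopping and switching by arm, time and reason. Add a delta-shift (missing-not-at-random) sensitivity analysis varied separately by arm.
5. If later data cannot be collected, drop the ITT label and state the on-treatment estimand.

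**Cost.** Protocol and SAP wording, sponsor and ethics committee approval (section 8, Plan modification), and at most five already scheduled visits per affected child. No extra enrolment is proposed. The headline effect may be smaller, and power with it. Using Φ(d/(0.40 × √(2/n)) − 1.96), with d from the two control-rate rows of the table (no-month-9 case in brackets):

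| Stopping in RLRL arm | 86 per arm | 96 per arm |
|---|---|---|
| 10% | 86.9% (86.0%) | 90.2% (89.5%) |
| 20% | 82.2% (80.1%) | 86.1% (84.2%) |
| 30% | 76.6% (72.9%) | 81.0% (77.4%) |

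The right-hand column applies only if all 96 per arm are followed to 12 months.

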8.2 Plan modification

8.3 Informed consent

8.4 Confidentiality

1. ABSTRACT

Basic information on clinical practice of medical devices:

Device Classification: Class II medical devices

Specification Model: RS-200-1A

Date: September 20, 2020

Sponsor: Zuoguan Medical Devices Co., Ltd. at Suzhou Industrial Park

Practice Title

A Randomized, Controlled, Multi-centre Clinical Study on the Effectiveness and Safety of repeated low-level red-light (RLRL) for myopia control in children and adolescents with high myopia

Practice Purpose

A Study on assessing the effectiveness and safety of RLRL for myopia control in children and adolescents with high myopia.

Subject Population

Subject: Children aged 6-16 with at least one eye with myopia of cycloplegic spherical equivalent refraction (SER) at least -4.0 D

Sample size: 192 subjects are planned to be enrolled and assigned to the intervention group or control group according to a ratio of 1:1

Practice Design

Overall design:

This prospective, single-blind, parallel-group, multi-center randomized clinical trial was conducted at six tertiary hospitals. Participants between 6 and 16 years old with at least one eye with a spherical equivalent refraction (SER) of -4.0 D or greater were recruited. The enrolled participants were randomly placed at a 1:1 ratio into

intervention (RLRL treatment plus single-vision spectacles) or control (single-vision spectacles) groups. The participants attended follow-up appointments 1, 3, 6, 9, and 12 months after the baseline evaluation.

Outcomes:

1. Primary Outcome: Change of Axial length (AL, mm) at 12-month follow-up
2. Secondary Outcome: Change of cycloplegic spherical equivalent (SE, D) at 12-month follow-up
3. Optional Indicators:

Changes of uncorrected visual acuity (UCVA), best-corrected visual acuity (BCVA), intraocular pressure, etc.;

Changes of corneal thickness (CT), anterior chamber depth (ACD) and lens thickness (LT);

Observe macula and the structure of fundus around the optic disc;

Observe the choroid/retinal thickness of the fundus;

Compliance index: frequency of equipment uses.

Safety assessment

- ① Sudden vision loss;
- ② Afterimage time over 5 minutes;
- ③ Side effects such as glare, photophobia and flickering;
- ④ Structural damage to retina: tissue disruption or discontinuity, edema, or other abnormalities in the photosensory layer of the SS-OCT images;
- ⑤ Increased intraocular pressure etc.

Participants selection and exclusion criteria:

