3.4 Intervention

1. Intervention group: Use the Eyerising RLRL device to treat with the treatment device twice a day, three minutes each time, with an interval of 4 hours. The method of use is as follows:

- A. Put the instrument on a stable desktop, confirm the interface before connecting accessories;
- B. Connect the power supply and turn on the power switch;
- C. Let the user sit in a suitable position, loosen the hand-wheel on the side of the treatment device, and adjust it up and down to the most suitable angle to make the eyes relatively comfortable when resting on the goggles, and fix the hand-wheel to a fixed angle;
- D. Enter the subject's unique account and password, and click Confirm to log in;
- E. After logging in, the first interface enters the photo-kinetic energy treatment item by default, take off the glasses, click OK. Then, making sure that there is visible red light in the eye position corresponding to the instrument, and put the eyes close to the blue eye mask;
- F. For the first use, please place your hands on the top of the treatment device and adjust the interpupillary wheel on the top at the same time. It is better to regard the two light points as one light point. If not, the brightest light also can be used.
- G. After three minutes of use, the light kinetic energy will automatically stop, leave the blue eye mask, close your eyes and rest for 3-5 minutes, until the front and back image spots disappear;

H. After using the instrument, turn it off.

2. Control group: single vision spectacle lenses

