3.5 Outcomes

1. Primary Outcome: Change of Axial length (AL, mm) at 12-month follow-up
2. Secondary Outcome: Change of cycloplegic spherical equivalent (SE, D) at 12-month follow-up
3. Optional Indicators:

Changes of uncorrected visual acuity (UCVA), best-corrected visual acuity (BCVA), intraocular pressure, etc.;

Changes of corneal thickness (CT), anterior chamber depth (ACD) and lens thickness (LT);

Observe macula and the structure of fundus around the optic disc;

Observe the choroid/retinal thickness of the fundus;

Compliance index: frequency of equipment uses.

[figure not shown]

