Eyerising amblyopia comprehensive treatment instrument is mainly composed of treatment module, housing, eye mask, interpupillary distance adjustment knob, locking hand wheel, touch screen, control circuit, and electrical interface (as shown in Figure 1). The functions of each component structure are as follows:

- 1) Treatment module: an electronic module that realizes four treatment functions;
- 2) Shell: fix and install each component module, which is convenient for users to use the instrument;
- 3) Eye mask: The user's eyes are close to the eye mask during treatment, and the eye mask has a good wrapping property to prevent the interference of external light;
- 4) Interpupillary distance knob: The treatment device is a binocular product, and the user can adjust the distance of the emission window of the treatment device to be consistent with their own interpupillary distance, to achieve the best treatment effect;
- 5) Hand wheel lock: The user adjusts the pitch angle of the treatment head to the best position according to his height and posture, and then locks it with the hand wheel

lock to prevent loosening.

- 6) Touch screen: the user operates the machine through the touch screen;
- 7) Circuit control: control each electronic module;
- 8) Electrical interface: including power switch, power interface, USB interface and LAN interface.
- 9) Power switch: use for starting and closing the machine;
- 10) Power interface: connect the adapter for power supply;
- 11) USB interface: used for manufacturers to detect and debug internal circuits;
- 12) LAN interface: help machine connect to the external Internet.

Figure 1:

治疗眼罩: Treatment Eye Mask

激光辐射窗口: Laser Radiation Window

锁紧手轮: Hand Wheel Lock

触摸屏: Touch Screen

外壳: Shell

2. Specifications and models

RS-200-1A

3. Working principle and mechanism

The potential of low-intensity photochemical conversion can cause photochemical reactions in the retina, including increasing the activity of cytochrome C oxidase, changing gene expression to regulate the mitochondrial respiratory chain, and increasing the biological activity of nitric oxide. Also, it can increase Choroidal metabolism rate and circulation to improve scleral hypoxia, prevent or slow down the progression of myopia.

4. product indications and contraindications, precautions,

Indications:

- 1) It is suitable for patients with ametropia, anisometropia and strabismus amblyopia.
- 2) It is suitable for the treatment of juvenile myopia.

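### The one-eye rule in section 5.2 is not limited to efficacy, so on its plain reading the acuity and IOP summaries omit one of two exposed eyes per RLRL child

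*Combined protocol and SAP*

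**What the plan says.** **Exposure.** The device description after the reference list states: "The treatment device is a binocular product". The operating steps in section 3.4 agree, since the child looks at two beams: "It is better to regard the two light points as one light point". Every RLRL child is therefore exposed in both eyes at each session.

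**Eye selection.** The first paragraph of section 5.2 has two rules. For one qualifying eye: "If a participant had only one eye with a SER exceeding -4.0 D, that eye was selected for the statistical analysis". For two: "In cases where both eyes were exceeding -4.0 D, the right eye was chosen for the analysis". Neither sentence names an outcome or exempts one.

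**Outcomes that follow in section 5.2.** IOP change is modelled as a secondary outcome alongside SER, with random effects for the participant and no eye-level term. UCVA change is put into three categories. For BCVA the text is: "The BCVA at the 12-month and baseline was evaluated against the 20/25 standard". None of these gives a unit of analysis of its own. Section 3.5 places all three measures under optional indicators: "Changes of uncorrected visual acuity (UCVA), best-corrected visual acuity (BCVA), intraocular pressure, etc".

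**Safety.** A separate paragraph of section 5.2 places the safety analyses in the ITT population, has adverse events reported one by one, and has six ophthalmologists read the OCT scans. It sets no eye restriction. The abstract's safety list includes "Sudden vision loss", retinal structural damage and raised IOP, again without naming an eye.

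**The concern.** One eye per child is a sound choice for axial length and refraction, because it avoids correlated observations in the efficacy model. It suits harm less well when both eyes receive the exposure. If a child analysed on the right eye slowly loses best-corrected acuity in the left, or has a pressure rise only there, the acuity and IOP tables show nothing for that child.

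Safety is half of the stated purpose in section 2.3. BCVA is the plan's only measure of best-corrected visual function, and raised IOP is on both of its safety lists (abstract and section 4.2). A table built on selected eyes could be read as saying how many children were affected, when it can say only how many selected eyes were.

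**Working it through.** **Inputs from the documents.** 96 children per arm (section 3); two eyes exposed per RLRL child; one eye selected per child (section 5.2). The sample-size inputs in section 3.6 are alpha 0.05, power 90%, SD 0.40 mm and difference 0.20 mm.

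**Inputs assumed.** The documents give no per-eye event rate and no between-eye correlation (rho). Both are shown as ranges.

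**1. The plan's own figure.** With two-sided alpha, the normal approximation is n = 2 × (1.960 + 1.282)² × (0.40/0.20)² = 84.06, so 85 per arm. The two-sample t calculation gives 85.03, so 86 per arm, as stated. Then 86/0.9 = 95.6, so 96 per arm and 192 in total. This reproduces. It rests on axial length in one eye per child, so the eye rule for safety tables does not affect it.

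**2. Eyes kept.** In the RLRL arm 96 × 2 = 192 eyes are exposed and 96 are selected (50%). With 86 evaluable children it is 86 of 172 (50%). The share is the same whether one or both eyes qualify.

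**3. Precision if no event is seen.** One-sided 95% upper bound = 1 − 0.05^(1/n), where n = 96 for one eye per child and the effective n is about 2 × 96/(1 + rho) for both eyes.

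| Eyes used | rho | Effective n | Upper bound per eye |
|---|---|---|---|
| One per child | – | 96 | 3.07% |
| Both | 0 | 192 | 1.55% |
| Both | 0.5 | 128 | 2.31% |
| Both | 1 | 96 | 3.07% |

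The gain is a halving at best and nothing at worst.

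**4. Chance of seeing at least one event.** This is 1 − (1 − p)^n for an assumed per-eye rate p, comparing 96 eyes with 192 independent eyes (the most favourable case for using both):

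- p = 0.5%: 38.2% against 61.8%
- p = 1%: 61.9% against 85.5%
- p = 2%: 85.6% against 97.9%

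**5. Per-eye rate against per-child count.** If both eyes carry the same risk p, the selected eye estimates p without bias. The risk that a child is affected in either eye is 2p − [p² + rho × p(1 − p)]. With p = 1%:

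- rho = 0: 2% − 0.01% = 1.99%, of which the selected eye shows 1%
- rho = 0.5: 2% − 0.505% = 1.495%, of which it shows 1%
- rho = 1: 2% − 1% = 1%, all of which it shows

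So between none and about half of affected children are missing from a one-eye table. Where the loss is strictly one-sided and equally likely in either eye, half are missing.

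**6. Other routes by which a fellow-eye change could appear.** The abstract lists sudden vision loss, and the safety list in section 4.2 has reduced near acuity. Gradual loss of distance BCVA is on neither. Raised IOP is on both, but no size of IOP or BCVA change is set that makes it an adverse event. Adverse events are recorded for both arms at each follow-up visit, but the side-effect questionnaire in section 4.2 goes only to the intervention group. OCT is scheduled at screening, 6 and 12 months, though section 4.2 marks it optional.

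**The case against.** The strongest reply is that section 5.2 nowhere says the eye rule governs safety. The rule stands in the population paragraph, just before the efficacy models. The safety paragraph is separate and unrestricted by eye, and the documents do not label BCVA or UCVA a safety endpoint. Fellow-eye sudden vision loss, structural damage or raised IOP is already a listed safety item. Choosing the right eye does not depend on outcome and is the same in both arms, so it costs precision and introduces no bias. Both eyes of a child share the same device and sessions, so rho may be well above zero and the gain small.

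Most of this stands, and it rules out three stronger readings. A reader might infer that half of all visual-safety data is discarded; adverse-event reporting and OCT reading are not limited to the selected eye, so it is not. A reader might infer that the per-eye result is biased towards reassurance; under equal risk it is not. A reader might also take "Either eye meets the diagnosis of myopic refractive error" to mean the fellow eye is largely unscreened. The BCVA entry limit may indeed not reach that eye, but the ocular exclusions are not confined to one eye, and a poor baseline would not hide a change from baseline.

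The reply does not show that the acuity and IOP summaries use both eyes. No sentence says so, the rule has no exception, and a model with participant-level random effects only fits one eye per child. Individually listed events are also not a between-arm comparison of measured change.

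**Conclusion.** The point holds for the BCVA summary, the UCVA categories and the modelled IOP change. Followed as written, the plan bases these on 96 of 192 exposed eyes in the RLRL arm, and a gradual one-sided change in the unselected eye would be missing unless someone reported it. The consequence is an understated either-eye count per child and some loss of precision: a zero-event bound of 3.07% per eye, against 1.55% to 3.07% with both eyes, depending on rho.

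This rests on two things. One is reading an unqualified rule as applying to outcomes that name no eye, which is an inference, though the natural one. The other is the assumed ranges for event rate and rho. The plan should be changed, but neither the primary analysis nor the sample size is affected.

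**What to change.** In section 5.2:

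- Limit the single-eye rule to the AL and SER efficacy models.
- Summarise BCVA change, UCVA category and IOP change by arm for both eyes of every randomised child with follow-up data. Report per child (event in either eye, worse-eye change) and per eye, allowing for within-child correlation.
- State what counts as an event in these tables. The plan already has a BCVA threshold and UCVA line categories, but nothing equivalent for IOP.
- State that adverse events and OCT findings cover both eyes.
- Confirm that acuity and IOP are recorded for both eyes. Among the measurements in section 4.2, only axial length is explicitly taken on both.

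The cost is SAP wording and a few more tables. Acuity and IOP are already scheduled and the sample size does not change. The downside is that event counts may look less favourable. If both-eye summaries were always intended, one clarifying sentence and the per-child definition would settle it.
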